Vasculitides	Large vessels vasculitis (including giant cell arthritis such as Takayasu's arthritis and temporal arthritis), medium sized and /or small vessels vasculitis (including poly arthritis no dose, Kawasaki's disease, microscopic polyangitis, Wegener's granule atoms is, Churg-Strauss syndrome (allergic granulomatous angiitis), Buerger's disease (thromboangiitis obliterans), necrotizing vasculitis and ANCA-positive vasculitis (type unspecified), Henoch-Schonlein purpura, Bechet's syndrome, leukocytoclastic vasculitis)
Gastrointestinal Disorders	Crohn's disease, celiac disease, ulcerative colitis, ulcerative proctitis.
Hepatic Disorders	Autoimmune hepatitis, autoimmune cholangitis, primary sclerosis cholangitis, primary biliary cirrhosis
Renal Disorders	Autoimmune glomerulonephritis (including IgA nephropathy, glomerulonephritis rapidly progressive, membranous glomerulonephritis, membranoproliferative glomerulonephritis, and mesangioproliferative glomerulonephritis)
Cardiac Disorders	Autoimmune myocarditis/cardiomyopathy

Skin Disorders	Alopecia areata, psoriasis, vitiligo, Raynaud's phenomenon, erythema no do sun, autoimmune bulbous skin disease (including pemphigus, pemphigoid and dermatitis herpetiformis), cutaneous lupus erythematosus, morphed, lichen plants, Stevens-Johnson syndrome, Sweet's syndrome
Hematologic Disorders	Autoimmune hemolytic anemia, autoimmune thrombocytopenia, antiphospholipid syndrome, thrombocytopenia
Metabolic Disorders	Autoimmune thyroiditis, Grave's or Basedow's disease, new onset Hashimoto thyroiditis, diabetes mellitus type 1, Addison's disease
Other Disorders	Goodpasture syndrome, idiopathic pulmonary fibrosis, pernicious anemia, sarcoidosis.

Abbreviations: ANCA: anti-neutrophil cytoplasmic antibody, IgA: immunoglobulin A.

9.5.6.6 Assessment of Severity

All AEs, except AEs in e-diary card, will be assessed according to the US NCI Common Terminology Criteria for Adverse Events (CTCAE) 5.0 (published on November 27, 2017) associated with the AE term. The following standard with 5 grades is to be used to measure the severity of adverse events in this study.

Table 9-7 Intensity scales of AE

Grades of AE	Description
Grade 1	Mild; asymptomatic or mild symptoms; clinical or diagnostic observations only; intervention not indicated.
Grade 2	Moderate; minimal, local or noninvasive intervention indicated; limiting age-appropriate instrumental ADL*
Grade 3	Severe or medically significant but not immediately life-threatening; hospitalization or prolongation of hospitalization indicated; disabling, limiting self care ADL**
Grade 4	Life-threatening consequences; urgent intervention indicated.
Grade 5	Death related to AE.

* Instrumental activities of daily living (ADL) refer to preparing meals, shopping for groceries or clothes, using the telephone, managing money, etc.

** Self-care ADL refer to bathing, dressing and undressing, feeding self, using the toilet, taking medication, and not bedridden.

9.5.6.7 The Relationship to Study Vaccine

The investigator will make an assessment of the relationship between investigational vaccine and the occurrence of each AE/SAE, except solicited reactions to vaccination. The reasonable possibility will be determined based on the investigator's clinical judgment. The causality should be considered as one of the categories described below.

Table 9-8 The relationship between AE and study vaccine

Causality term	Assessment criteria
Certain	
 ● Event or laboratory test abnormality, with plausible time relationship to drug intake ● Cannot be explained by disease or other drugs ● Response to withdrawal plausible (pharmacologically, pathologically) ● Event definitive pharmacologically or phenomenologically (i.e. an objective and specific medical disorder or a recognized pharmacological phenomenon) ● Rechallenge satisfactory, if necessary
Probable / Likely	
 ● Event or laboratory test abnormality, with reasonable time relationship to drug intake ● Unlikely to be attributed to disease or other drugs ● Response to withdrawal clinically reasonable ● Rechallenge not required
Possible	
 ● Event or laboratory test abnormality, with reasonable time relationship to drug intake ● Could also be explained by disease or other drugs ● Information on drug withdrawal may be lacking or unclear
Unlikely	
 ● Event or laboratory test abnormality, with a time to drug intake that makes a relationship improbable (but not impossible) ● Disease or other drugs provide plausible explanations
Unrelated	
 ● Occurred before dosing ● Due wholly to factors other than study treatment

Each event should be followed until resolution or the event is considered stable. Both regular return and telephone contact will be acceptable.

9.5.6.8 Adverse Events Reporting

Documentation and Reporting of Adverse Events

All investigators should follow up subjects with AEs until the event is resolved or until, in the opinion of the investigator, the event is stabilized or determined to be chronic. Details of AE resolution must be documented in the CRF.

All AEs should be reported and documented in accordance with the procedures outlined in this section. All AEs occurring during the study must be documented on the relevant CRF pages.

Reporting of Serious Adverse Events

Any SAE must be reported by the investigator if it occurs during the clinical study, whether or not the SAE is considered to be related to the investigational product. An SAE report consists of the SAE form, the AE form, and the concomitant medication form. A copy of these forms must be emailed **within 24 hours** to Contract Research Organization (CRO), StatPlus Inc., and StatPlus will inform United Biomedical, Inc., Asia on the same day.

The investigator should not wait to receive additional information to document fully the event before notification of a SAE, though additional information may be requested. Where applicable, information from relevant laboratory results, hospital case records, and autopsy reports should be obtained.

Instances of death, congenital abnormality, or an event that is of such clinical concern as to influence the overall assessment of safety, if brought to the attention of the investigator at any time after cessation of study agent administration and linked by the investigator to this study, should be reported to the study monitor.

The sponsor and/or the appointed representative(s) will promptly notify all relevant investigators and the regulatory authorities of findings that could adversely affect the safety of subjects, impact on the conduct of the study, or alter the IEC/ IRB approval/favorable opinion of the study. In addition, the sponsor and/or the appointed representative(s), will expedite the reporting to all concerned investigators, to the IEC(s)/IRB(s), where required, and to the regulatory authorities of all adverse reactions that are both serious and unexpected.

Details of the procedures to be followed if a pregnancy occurs are also provided in Section 7.4.8.4.

Documentation and Reporting of SUSARs

All suspected unexpected serious adverse reactions (SUSARs) will be the subject of expedited reporting. The sponsor and/or the appointed representative(s) shall ensure that all relevant information about a SUSAR that is fatal or life-threatening is reported to the relevant competent authorities and IEC/IRB within 7 days after knowledge by the sponsor of such a case and that relevant follow-up information is communicated within an additional 8 days. All other SUSARs will be reported to the relevant competent authorities and IEC/IRB within 15 days after knowledge by the sponsor of such a case. All investigators should follow up SUSARs until the event is resolved or until, in the opinion of the investigator, the event is stabilized or determined to be chronic. Poststudy SUSARs that occur after the subject has completed the clinical study must be reported by the investigator to the sponsor.

Documentation and Reporting of SARS-CoV-2 infection

All subjects will be surveilled for potential COVID-19 illness from Visit 1 onwards. Potential COVID-19 illnesses and their sequelae that are consistent with the clinical endpoint definition should not be recorded as AEs or SAEs, even though the event may meet the definition of an SAE. These data will be captured as efficacy assessment data only on the relevant pages of the CRF, as these are expected endpoints.

Potential COVID-19 illness events and their sequelae will be reviewed by IDMC. Any SAE that is determined by the IDMC not to meet endpoint criteria is reported back to the SAE reporting process. The investigator's SAE awareness date is the date on which events is confirmed not to meet endpoint criteria.

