7.4.7 Blinding

This is an observer-blind study, as the physical appearance of the investigational vaccine candidates and the placebo may differ. Only the dispenser(s)/administrator(s) will be unblinded. These study staffs are responsible for receiving, dispensing, preparing and administering the study intervention. The investigational products should be administered in a manner that prevents the subjects to identifying their treatment based on vaccine physical appearance. The dispenser(s)/administrator(s) should not participate in any of the study clinical evaluations or assay, and keep minimum contacts with other study personnel.

Neither the subjects nor the investigators, sponsor staffs, clinical monitors, study coordinators other than dispenser(s)/administrator(s), or other site staff who involve in clinical evaluation of the subjects will be aware of the treatment received either at the time of randomization or later, throughout the conduct of the trial. **These study personnel will be blinded until Visit 5. Unblinding will be carried out via disclosed Randomization Envelop during Visit 5.**

The treatment codes will be not prematurely broken unless an emergency situation, when the appropriate management of the subject necessitated knowledge of the treatment allocation, occurred. In the event of a medical emergency, if possible, the clinical monitor should be contacted before the treatment code blind is broken to discuss the need for unblinding. For unblinding a

subject, the treatment code blind can be obtained by the investigator, by opening the emergency envelope.

The sponsor must be notified immediately if the treatment code blind is broken. The date, time, and reason that the blind is broken must be recorded in the source document and the same information (except the time) must be recorded on the eCRF.

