9.5.7 Immunogenicity Assessments

9.5.7.1 Surveillance and Laboratory Diagnosis of SARS-CoV-2 Infection during Clinical Trial

During the observation period of the clinical trial, the participants with fever, cough and other respiratory symptoms should immediately go to the designated hospital. The doctor or investigator may collect the nasopharyngeal/throat swabs and to perform CT and other imaging examinations to analyse whether it is caused by SARS-CoV-2 infection. In the event of SARS-CoV-2's infection during the clinical trial, it is necessary to conduct a case investigation, and the critically ill or dead cases need to continue to conduct a special investigation, mainly to analyze whether there is an ADE or VAERD phenomenon. Subjects encountered the medical condition listed in Table 9-5 should also check HLA and SARS-CoV-2 infection,

In addition to SARS-CoV-2 nucleic acid detection, multiple pathogens will be detected for differential diagnosis of swabs. The detail of detectable pathogens of test kit will be listed below:

- ✓ Adenovirus
- ✓ Coronavirus 229E
- ✓ Coronavirus HKU1
- ✓ Coronavirus NL63
- ✓ Coronavirus OC43
- ✓ Human Metapneumovirus
- ✓ Human Rhinovirus/Enterovirus
- ✓ Influenza virus A
- ✓ Influenza virus B
- ✓ Parainfluenza virus 1
- ✓ Parainfluenza virus 2
- ✓ Parainfluenza virus 3
- ✓ Parainfluenza virus 4

- ✓ Respiratory syncytial virus
- ✓ Bordetella parapertussis
- ✓ Bordetella pertussis
- ✓ Chlamydia pneumoniae
- ✓ Mycoplasma pneumoniae

The potential SARS-CoV-2 infection will be reviewed by IDMC.

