9.6 Independent Data Monitoring Committee (IDMC)

The Independent Data Monitoring Committee (IDMC) will act in an expert, independent advisory capacity to monitor participant safety and evaluate the efficacy of UB-612 vaccine against COVID-19 in this study. The IDMC will consist of at least two physicians and one statistician. An IDMC meeting will be held at:

- (1) 1st time: when all adult immunogenicity data (350 evaluable young adults and 154 evaluable elderly subjects) for Day 57 are available
- (2) 2nd time: when at least half of core group subjects will be completed Day 85 safety follow up. Adolescence could be enrolled after 2nd IDMC meeting.
- (3) 3rd time: when all immunogenicity data for lot-to lot consistency of Day 57 are available.
- (4) 4th time: when 350 evaluable adolescents will be completed Day 57 safety follow up.

The meeting schedule might be adjusted based on the progress of recruitment. The IDMC meetings may also be held at any time point if any situations after vaccination meet the study stopping criteria or when the sponsor considers it necessary. Unscheduled IDMC meetings may also be held if any potential COVID-19 illness events or obvious situations for the deterioration the subject safety or study conduct occur.

Responsibilities of the IDMC include the following:

- ✓ Protect the safety and confidentiality of the study participants;

- ✓ Evaluate the quality and validity of the data generated in this study;
- ✓ Consider factors external to the study when relevant information becomes available, such as scientific or therapeutic developments that may have an impact on the safety of the participants or the ethics of the trial;
- ✓ Make recommendations to the Sponsor and the Principal Investigator (PI) concerning continuation, termination or other modifications of the study based on factors including overwhelming effectiveness, futility or safety issues;
- ✓ Make recommendations and assist in the resolution of problems reported by the PI;
- ✓ Assist sponsor by commenting on any problems with study conduct and/or data collection;
- ✓ Maintain confidentiality regarding the study outside the IDMC (including, but not limited to the investigators, IRBs, regulatory agencies, or sponsor) except as authorized by the IDMC.

Detailed description of the IDMC responsibilities, data reviewed, meeting process, considerations and policies will be described in a separate IDMC charter.

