9.6.1 Overall Study Stopping Rules

The following stopping rules are in place for all subjects, based on review of AE data and e-diary reactogenicity data.

1. An SAE that is assessed by the investigator as possibly related, or for which there is no alternative, plausible, attributable cause.
2. A Grade 4 local reaction, systemic adverse event or fever that is assessed as possibly related by the investigator, or for which there is no alternative, plausible, attributable cause.
3. If any 3 subjects vaccinated with UB-612 (at any dose level) report the same or similar* severe (Grade 3) AE (including laboratory abnormalities), assessed as possibly related by the investigator, or for which there is no alternative, plausible, attributable cause.

* defined as same preferred term of current MedDRA

4. If a stopping rule is met, further dosing will be paused and the IDMC will determine whether dosing should resume.
5. If two of the same or similar *SAEs or Grade 4 local or systemic reactions occur, dosing will be suspended and both the IDMC and regulatory authorities will be consulted before resumption of dosing.

* defined as same preferred term of current MedDRA

In the event that a stopping rule is met, the following actions will be taken:

- The stopping rule will PAUSE randomization and administration of study vaccine at all dose levels and all treatment groups.
- The IDMC will review the relevant safety data.

- For all subjects already vaccinated, all other routine study conduct activities, including ongoing data entry, reporting of AEs, electronic diary completion, blood sample collection, and subject follow-up, will continue during the pause.
- Data from placebo recipients will not contribute to the stopping rules.
- Electronic diary data confirmed by the investigator as having been entered in error will not contribute toward a stopping rule.

Should the study be terminated prematurely, the sponsor will provide written notification to all investigators and regulatory authorities specifying the reason(s) for early termination. The investigator must inform the institutional review board (IRB)/independent ethics committees (IEC) promptly and provide the reason(s) for the termination. Previously dosed subjects will be assessed through all planned study safety visits.

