10.9 Interim Analysis

Six interim analyses and reports will be performed when (1) adult immunogenicity data (350 evaluable young adults and 154 evaluable elderly subjects) for Day 57 are available; (2) at least half of core group subjects (at least 3500 evaluable subjects) will be completed Day 85 safety follow up, as EUA application dossier; (3) all immunogenicity data for lot-to lot consistency of Day 57 are available, EUA application dossier; (4) 350 evaluable adolescents completed Day 57 safety follow up, as supplementary dossier for EUA; **(5) immunogenicity and safety data for young and elderly adult subjects receiving 3rd vaccination completed Visit 7, which is 14 days after 3rd vaccination; (6) immunogenicity and safety data for adolescent subjects receiving 3rd vaccination completed Visit 7, which is 14 days after 3rd vaccination.**

The first four analyses and reports will be analysed and drafted by the unblinded statistician, reviewed by the IDMC, and submitted to appropriate regulatory authorities for review if as EUA application dossier or supplementary dossier for EUA.

For the evaluation of safety, immunogenicity, and lot-to-lot consistency, the following endpoints will be included in the first four interim analyses.

- Local reactions, systemic events, unsolicited AEs, and SAEs
- Changes of safety laboratory measures
- Changes of vital signs and physical examinations
- Seroconversion rate of SARS-CoV-2 neutralizing antibody and antigen-specific antibody (Anti-S1-RBD) on Day 57
- Geometric mean titer of SARS-CoV-2 neutralizing antibody and antigen-specific antibody (Anti-S1-RBD) on Day 57
- Geometric mean fold increase in SARS-CoV-2 neutralizing antibody and antigen-specific antibody (Anti-S1-RBD) on Day 57
- Lot consistency by the comparisons of the GMT of SARS-CoV-2 neutralizing titers on Day 57 induced by 3 independent UB-612 vaccine clinical materials. The 95% confidence intervals between groups will be within the margin of 0.5 to 2.

For last two interim analyses (i.e., interim analysis (5) and (6)), the analyses demonstrate the immunogenicity and safety data on the adult and adolescent subjects received 3rd dose of UB-612 including (but not limited to) following endpoints.

- **Local reactions, systemic events, unsolicited AEs, and SAEs after 3rd dose of UB-612**
- **Changes of safety laboratory measures**
- **Changes of vital signs and physical examinations pre/post 3rd dose of UB-612**

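### V-205 gives the IDMC the decision on which serious illnesses leave the SAE record as COVID-19 endpoints, and nothing in the protocol masks that decision to treatment arm

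*Supplement*

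**What the plan says.** All references are to the V-205 protocol.

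- **Classification (9.5.6.8).** Potential COVID-19 illnesses and sequelae that fit the clinical endpoint definition "should not be recorded as AEs or SAEs, even though the event may meet the definition of an SAE"; they are captured as efficacy data only. Then the review is assigned: "Potential COVID-19 illness events and their sequelae will be reviewed by IDMC". For serious events a route back is added: "Any SAE that is determined by the IDMC not to meet endpoint criteria is reported back to the SAE reporting process". In those returned cases, the clock for SAE awareness starts only once endpoint status has been ruled out.
- **Repeated in 9.5.7.1.** "The potential SARS-CoV-2 infection will be reviewed by IDMC".
- **What the committee receives (10.9).** "The first four analyses and reports will be analysed and drafted by the unblinded statistician, reviewed by the IDMC".
- **What it advises on (9.6).** "continuation, termination or other modifications of the study based on factors including overwhelming effectiveness, futility or safety issues". Unscheduled meetings may be called for potential COVID-19 events. Details are left to a separate charter.
- **Stopping rules (9.6.1).** "Data from placebo recipients will not contribute to the stopping rules". The committee determines whether dosing resumes.
- **Blinding (7.4.7).** "Only the dispenser(s)/administrator(s) will be unblinded". The groups listed there as kept blind are subjects, investigators, sponsor staff, monitors, coordinators and other site staff. The IDMC is not named.
- **Endpoints (6.2, 6.6, 10.5.1, 10.7).** SAEs to Day 365 are a primary safety endpoint, compared between groups by Fisher's exact test. PCR-based COVID-19 incidence is exploratory and summarised descriptively.

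**The concern.** Classifying an event decides where it is counted. A serious event accepted as a COVID-19 endpoint leaves the SAE record; one that is turned down goes back into it. That sorting should not depend on the arm. Here it is given to the one body that, by its role, reviews comparative data while site and sponsor staff are blind. No separate adjudication group is described, and no order is set between classifying events and seeing by-arm results.

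At stake is chiefly the between-arm SAE comparison, a primary safety endpoint. There is also a knock-on effect within safety monitoring: an event held as an endpoint is not recorded as an SAE, so it may not reach the first stopping rule in 9.6.1, which is triggered by a possibly related SAE.

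**Working it through.** No sample size, power or error rate in the plan depends on this point, so the check is mainly a side-by-side reading, with a little arithmetic on what a decision does.

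1. **Who decides.** 9.5.6.8 names the IDMC for both the review and the endpoint-or-SAE determination; 9.5.7.1 repeats the review role.

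2. **What the IDMC may know.** It reviews the first four interim reports, prepared by an unblinded statistician (10.9). It may recommend stopping for effectiveness or futility (9.6), which needs results by arm. It rules on pauses that only vaccine recipients can trigger (9.6.1), so a triggered pause itself indicates the arm of the event. Access to allocation for every ill subject is not stated.

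3. **Is the classification masked?** 7.4.7 does not mention the IDMC. 11.2 withholds immunogenicity data from the blinded monitoring team only. The convalescent visit (8.4.4) collects anti-S1-RBD and neutralizing titres from subjects with potential illness, and titres can reveal the arm. No section withholds them from whoever classifies the event.

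4. **Where judgement remains.** In 8.4.1 a confirmed case is laboratory-defined, whatever the symptoms. That settles tested illnesses. It does not settle:
   - illnesses without a result: 8.4.2 calls for a PCR specimen, but 9.5.7.1 makes swabs optional and 8.4.3 records results only where they exist;
   - sequelae: whether a later event in a PCR-positive subject belongs to the illness is a clinical judgement;
   - the term clinical endpoint definition, which is not set out under that name.

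5. **Effect of one decision.** For arm g, let S = events recorded as SAEs and E = serious events held as COVID-19 endpoint data. Acceptance changes (S, E) by (−1, +1); rejection and return changes it by (+1, −1). S + E is unchanged either way. So one decision can favour one record at the expense of the other, and the combined count does not depend on the classification.

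6. **Scale.** Adults: 3850 × 6/7 = 3300 vaccine; 3850/7 = 550 placebo. One event is 1/3300 = 0.03 percentage points in the vaccine arm and 1/550 = 0.18 in the placebo arm. The ratio, 6, is simply the allocation ratio; it measures leverage per event, not bias.

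7. **Illustration on assumed counts.** Suppose equal true risk, with 12 vaccine and 2 placebo cases, and m vaccine cases turned down but no placebo cases. Apparent efficacy = 1 − [(12 − m)/3300] / (2/550). For m = 1, 3 and 6 this is 8%, 25% and 50%. The counts and the one-sided rejection are assumptions; the documents give neither.

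**The case against.** The strongest reply is that the protocol defers the committee's working methods to a charter that is not shown, and masked event listings are normal charter content. That stands as a limit: silence in the protocol does not prove that the review will be unmasked. But 9.5.6.8 assigns the task without any condition, and one sentence there would settle it.

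Second, a reader might infer that the IDMC knows the arm of each subject it classifies. The documents do not say so. The statistician is called unblinded, the report format is not described, and the statistician could drop placebo events before a stopping rule is raised. What stands is that a committee with by-arm results, ruling on vaccine-only triggers, can learn the arm of individual serious events and is not told to classify without it.

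Third, a reader might infer that efficacy and SAE results would both tilt toward the vaccine. Step 5 of the working rules that out for any single decision.

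Fourth, a reader might take the 8% to 50% illustration as a threat to the efficacy result. It is not an estimate. It would require PCR-positive vaccine cases to be turned down against the rule in 8.4.1, or a large share of untested ones, and the incidence endpoint carries no planned between-arm test.

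Fifth, two features cushion the safety side. Complications in Table 9-5 with a positive PCR are reported as AESIs under 9.5.6.5, and AESIs are also a primary safety endpoint. And placebo recipients are withdrawn at Visit 5, so later events have no concurrent control. Both stand. They narrow the concern without removing it, since sequelae outside Table 9-5 and illnesses without a positive PCR have no such backstop.

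**Conclusion.** The point holds as a gap in the protocol. Classification of serious potential COVID-19 events sits with a committee that sees comparative data, and nothing shown keeps the arm or the antibody titres out of that decision. It matters mainly for the primary SAE comparison while both arms are followed, up to Visit 5. It matters less for the exploratory incidence endpoint.

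The size of any bias cannot be computed, because event counts and the share needing judgement are not given; one adult event is 0.03 points in the vaccine arm or 0.18 in the placebo arm. The conclusion assumes that the IDMC's reports are by arm, which follows from its tasks but is not written, and that the charter does not already require masking. If the charter does, only the cross-reference is missing. The text does not show that biased classification will occur. The remedy is cheap enough that the sponsor should make the change.

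**What to change.** - In 9.5.6.8 and 9.5.7.1, and in the charter, state that case status follows the laboratory-confirmed rule of 8.4.1, and name that rule as the endpoint definition.
- State that any remaining judgement (illness without a test result, attribution of sequelae) is made on listings without treatment code or antibody titres, and is recorded and locked before the IDMC opens by-arm data, including at unscheduled meetings.
- Tabulate SAEs by arm twice: as recorded, and with added COVID-19 endpoint events that would otherwise meet the SAE definition. By step 5 of the working, the second table does not depend on the classification.

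The cost is a few sentences, a masked listing and one extra table. The downside is one more masked step before each closed session. No new committee, visit, sample or change in sample size is needed.
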